Engaging men from blue-collar industries in weight loss: Study 3- Evaluating the Acceptability of Weight Loss Treatments

Unique Protocol Identification Number: 18013105-IRB01

National Clinical Trial (NCT) Identified Number: NCT05386238

Principal Investigator: [name]

Sponsor: Rush University Medical Center

**Grant Title: Engaging men from blue-collar industries in weight loss: Tailoring
recruitment and treatment approaches**

Grant Number: K01DK119457

Funded by: NIDDKD

Version Number: v.1.000

11 May 2022

Title:

Engaging men from blue-collar industries in weight loss

Grant Number:

K01DK119457

Study Description:

Objectives*:

Primary Objective: Aim 1: Examine the acceptability of tailored behavioral weight loss program and a standard program in men working in blue-collar occupations.

Aim 2: Compare recruitment approaches that vary on trust-based messaging to recruit men with overweight/obesity who work in blue-collar occupations.

Secondary
Objectives:

Determine the feasibility of retaining participants to a randomized trial over six months.

Determine the reach of recruitment messages.

Endpoints*:

Primary Endpoint: Aim 1: Participant reported satisfaction at 3 months.

Aim 2: Proportion of participants who enroll in study by recruitment type.

| | |
|---|---|
| Secondary Endpoints: | Number of visits to recruitment websites by recruitment type. Participant reported satisfaction at 6 months. Percentage of participants who complete a weight assessment at the 6-month assessment timepoint. |
| Study Population: | Men working in blue-collar occupations with overweight or obesity. |
| Phase* or Stage: | Feasibility testing |
| Description of Sites/Facilities | Single site |
| Enrolling Participants: | |
| Description of Study Intervention/Experimental Manipulation: | This protocol is for a randomized pilot study that will test the acceptability of a novel weight loss program and a standard weight loss program in men with overweight or obesity who work in blue-collar occupations. The secondary aim of the study is to test in a randomized comparison the effect of recruitment messages that enhance trust in two ways: researcher trust enhancement (Yes, No) x participant endorsement (Yes, No). |
| Study Duration*: | 18 months |
| Participant Duration: | 6 months |

Table of Contents

| | |
|---|----|
| Statement of Compliance | 5 |
| Investigator's Signature | 5 |
| 1 Protocol Summary | 6 |
| 1.1 Synopsis | 6 |
| 1.2 Schema | 8 |

1 PROTOCOL SUMMARY

1.1 SYNOPSIS

[figure not shown]
| | | |
|--|--|---|
| Title: | Engaging men from blue-collar industries in weight loss | |
| Grant Number: | K01DK119457 | |
| Study Description: | | |
| Objectives*: | Primary Objective: | Aim 1: Examine the acceptability of tailored behavioral weight loss program and a standard program in men working in blue-collar occupations. Aim 2: Compare recruitment approaches that vary on trust-based messaging to recruit men with overweight/obesity who work in blue-collar occupations. |
| | Secondary Objectives: | Determine the feasibility of retaining participants to a randomized trial over six months. Determine the reach of recruitment messages. |
| Endpoints*: | Primary Endpoint: | Aim 1: Participant reported satisfaction at 3 months. Aim 2: Proportion of participants who enroll in study by recruitment type |
| | Secondary Endpoints: | Number of visits to recruitment websites by recruitment type. Percentage of participants who complete a weight assessment at the 6-month assessment timepoint. Participant reported satisfaction at 6 months. |
| Study Population: | Men BMI>25 | |
| Phase* or Stage: | Feasibility testing | |
| Description of Sites/Facilities Enrolling Participants: | Single site | |
| Description of Study Intervention/Experimenta l Manipulation: | This protocol is for a randomized pilot study that will test the acceptability of a novel weight loss program and a standard weight loss program in men with overweight or obesity who work in blue-collar occupations. The secondary aim of the study is to test in a randomized comparison the effect of recruitment messages that | |

enhance trust in two ways: researcher trust enhancement (Yes, No)
 endorsement (Yes, No).

Study Duration*: 18 months

Participant Duration: 6 months

1.2 SCHEMA

1.3 SCHEDULE OF ACTIVITIES

| | Screening | Baseline: | Time 3: | Time 6: | Reference | Measure type |
|---|-----------|-----------|-------------|---------|-----------|------------------|
| | Time 0 | Week 12 | Week 24 ± 4 | | | |
| | | | ± 4 | | | |
| Contact information | X | | | | | SR |
| Basic demographics | X | | | | | SR |
| Occupational situation | X | | X | X | | SR |
| Alcohol use | X | | | | 1 | SR |
| Physical activity readiness questionnaire | X | | | | 2 | SR |
| Weight | | X | X | X | | Physical measure |
| Waist circumference | | X | X | X | | Physical measure |
| Physical activity | | X | X | X | 3 | Staff interview |
| Program satisfaction | | | X | X | 4 | SR |
| Healthcare climate questionnaire | | | X | X | 5 | SR |
| Program satisfaction interview | | | | X | | Interview |
| Sugary beverage screener | X | X | | | 6 | SR |
| Fast food screener | X | X | | | 7 | SR |
| NCI Fruit and Vegetable Screener | X | X | | X | 8 | SR |
| Weight loss strategies | X | X | | X | 9 | SR |
| Self-weighing frequency | X | X | | X | 10 | SR |
| Food shopping habits | X | X | | X | 11 | SR |

| | | | |
|---|---|---|-----------------|
| Adverse Events Reporting | X | X | SR |
| Sessions attended | X | X | Staff report |
| Tracking submitted | X | X | Staff report |
| Demographics | X | | SR |
| Patient preference for treatment | X | | SR |
| Weight loss history/Motivations for weight loss | X | | SR |
| Tobacco use | X | | SR |
| Health literacy | X | | ¹² . |
| Delay discounting | X | | ¹³ . |
| Medical conditions | X | | SR |

2 INTRODUCTION

2.1 STUDY RATIONALE

Men working in blue-collar occupations have a high prevalence of overweight and obesity and have high rates of comorbidities associated with obesity. Unfortunately, these men are unlikely to participate in evidenced-based weight loss interventions. Further, few efficacious interventions have been developed that target this population for weight control.

The purpose of this study is to test the feasibility and acceptability of tailored recruitment messages and a novel, tailored behavioral weight loss intervention in the context of a randomized trial.

2.2 BACKGROUND

The prevalence of obesity has reached an all-time high in the United States,¹⁴ and the connection between obesity and numerous comorbidities and excess mortality has been well established.^{15 16 17} The combined prevalence of overweight and obesity is greater in men than women (79.2 vs. 76.8%),¹⁸ and both genders experience various related conditions, including diabetes, heart disease and stroke, and some cancers.^{2 3 4} Despite these similar risks, men are significantly less likely than women to attempt weight loss,¹⁹ participate in behavioral weight loss research studies^{20 21} or commercial weight loss programs,²² or bariatric surgery²³.

One subgroup of men with especially low participation rates in weight loss programs includes those working in blue-collar industries, which the U.S. Department of Labor defines as “precision production, craft, and repair occupations; machine operators and inspectors; transportation and moving occupations; handlers, equipment cleaners, helpers, and laborers.”²⁴ These industries are male-dominated, and men who work in these industries are at increased risk for obesity and related comorbidities compared to the general population.^{25 26 27} For example, the prevalence of type 2 diabetes is twice as high among truck drivers compared to the general population.²⁶ Compared to other industries, overweight or obesity in blue-collar industries yields greater reduction in job performance and productivity, increases risk for injury, and generates higher indirect costs associated with obesity (e.g., costs due to absenteeism).^{28 29} Together, these data indicate men from blue-collar industries would greatly benefit from participation in weight loss programs.

Men-only weight loss programs that integrate men’s preferences have begun to be developed and evaluated. In a meta-analysis and a systematic review, these programs led to increased weight loss compared to no intervention.^{30 31} My prior work adds to this literature³². Collectively, growing evidence suggests this type of weight loss program has higher acceptability to men than traditional approaches.

A glaring limitation of the male-targeted weight loss studies conducted thus far is that they are comprised primarily of men with high levels of education. The exact occupational representation of these samples is difficult to quantify because occupational background is rarely assessed in health research.³³ However, because only 7% of individuals working in blue-collar industries hold a Bachelor's degree,³⁴ this educational threshold can be used as an indicator of an *absence* of individuals working in blue-collar industries. Like many other men-only weight loss programs, my previous intervention was applied to a highly educated sample in which 83% of participants had at least a college degree. Because research on men's weight loss has predominately been conducted with a small, potentially non-representative subgroup of men, we cannot assume these programs will work equally well among men from blue-collar industries.

Tailoring interventions to occupational groups may be an effective way to reach underserved populations. Occupational groups have shared common experiences and social norms that promote/inhibit health behaviors.^{33 35} Addressing these experiences and norms may be an effective way to tailor programs but the efficacy of this tailoring is not known. First, health promotion programs targeting blue-collar occupations may need to tailor content considering the masculine norms, including a drive towards independence and eating "masculine" foods, which are highly prevalent in this group.³⁶ ³⁷ . [Mahalik & Burns, 2011](#); [Mahalik, Burns, & Syzdek, 2007](#); [Roos, Prattala, & Koski, 2001](#)) How to do this is not currently known. Second, workers in blue-collar occupations are at increased risk for injury, especially musculoskeletal injuries;([Charles, Ma, Burchfiel, & Dong, 2017](#); [Dembe, Erickson, & Delbos, 2004](#); [Farnacio, Pratt, Marshall, & Gruber, 2017](#); [Ma et al., 2018](#)) thus, inclusion of injury prevention strategies may be a key consideration. Research has demonstrated this is an effective strategy for smoking cessation([Sorensen et al., 2002](#)) but has not been tested for weight loss. Third, blue-collar occupations often, but not always, include high levels of physical activity. A common misperception among individuals in high-activity occupations is that they have a reduced need for leisure-time physical activity.([Caban-Martinez et al., 2014](#)) However, multiple studies have shown that higher occupational physical activity is associated with increased all-cause mortality in men even when controlling for other health behaviors (e.g. smoking).([Clays et al., 2013](#); [Coenen et al., 2018](#); [Harari, Green, & Zelber-Sagi, 2015](#); [Wang, Arah, Kauhanen, & Krause, 2016](#)) Leisure-time physical activity reduces this risk; ([Clays et al., 2013](#); [Harari et al., 2015](#); [Wang et al., 2016](#)) therefore, explicitly promoting the need for leisure-time physical activity, regardless of occupational activity may be needed. Finally, many workers in blue-collar industries report few options for healthy foods at work,([Nagler, Viswanath, Ebbeling, Stoddard, & Sorensen, 2013](#)) which has been confirmed by objective assessments of work environments.([Apostolopoulos et al., 2011](#); [Shimotsu, French, Gerlach, & Hannan, 2007](#)) Providing guidance on selecting healthy foods in this challenging setting may be an important feature of a tailored intervention; but again, this has not been demonstrated.

In preparation for this study, we have conducted formative studies that have focused on evaluating preferences men working in blue-collar occupations have for weight loss programs. These studies ([name] et al., under review and in preparation) have indicated that to reach this population, the intervention

should be delivered online, easily incorporated into their daily lifestyles, and be presented in a trustworthy fashion. There was little support for programs conducted in worksites indicating a need to reach this population at home (versus work). As a result, this study will use a randomized design to test the acceptability of an intervention that incorporating these program features into a novel, tailored intervention. Additionally, this study will incorporate factors found to be important to participants into recruitment messages.

2.3 RISK/BENEFIT ASSESSMENT

2.3.1 KNOWN POTENTIAL RISKS

The foreseeable physical, psychosocial, legal, and financial risks associated with participation in this study are minimal. There are minimal risks for individuals who receive the mailings as no personal health information will be included. The physical risks associated with participating in the intervention include an increased risk minor injury due to increasing leisure-time physical activity. This risk has been minimized by prescribing a gradual increase in physical activity, recommending walking as the primary form of physical activity, and repeated discussion of maintaining safety while exercising. Study assessments include widely used questionnaire measures. There is a very small chance that some items could be mildly distressing. In this event, subjects may postpone answering or opt out of distressing questions.

There is a risk of loss of confidentiality of participant data. Steps will be taken to maximize confidentiality of data . Also, other participants who attend the group-based weight loss program may share information about their interactions with you outside of the group. The research team will ask all group members to respect each other's privacy, but cannot guarantee they will do so.

There are no foreseeable legal or financial risks associated with participation.

2.3.2 KNOWN POTENTIAL BENEFITS

Subjects may experience an improvement via weight loss. Subjects participating in the post-intervention interviews are not expected to directly benefit from that component of the study. The potential benefits to future participants are that this study may advance the knowledge of the development and promotion behavioral weight loss interventions to reach and engage men from blue-collar industries.

2.3.3 ASSESSMENT OF POTENTIAL RISKS AND BENEFITS

There are minimal risks associated with this study and the potential benefits to both the participant and society outweigh the potential risks. This study has the potential to provide information on how to best reach and engage men working in blue-collar occupations in behavioral weight loss program. This is important due to the high rates of overweight and obesity in this population and the very low levels of

Engaging men from blue-collar industries in weight loss: Study 3- Evaluating the Acceptability of
Weight Loss Treatments
Protocol 18013105-IRB01
participation in weight control efforts.

Version 1.000

11 May 2022

3 OBJECTIVES AND ENDPOINTS

| OBJECTIVES | ENDPOINTS | JUSTIFICATION FOR ENDPOINTS |
|--|--|--|
| Primary | | |
| Aim 1: Examine the acceptability of tailored behavioral weight loss program and a standard program in men working in blue-collar occupations. | Participant reported satisfaction with program acceptability at 3 months. | Participant satisfaction is a proxy for program acceptability. |
| Aim 2: Compare recruitment approaches that vary on trust-based messaging to recruit men with overweight/obesity who work in blue-collar occupations. | Proportion of participants who enroll in study by recruitment message type. | The goal of recruitment is enrollment in the study. Using the proportion of participants who received the postcard as the endpoint provides an assessment of the effectiveness of the message. |
| Secondary | | |
| Determine the feasibility of retaining participants to a randomized trial over six months. | Percentage of participants who complete a weight assessment at the 6-month assessment timepoint. | High retention to the study will indicate the study procedures are feasible for a fully powered trial. |
| Determine the reach of recruitment messages. | Number of visits to recruitment websites. | The website is the first indication of participant interest in the study. |
| Determine the acceptability of the intervention. | Participant reported satisfaction with program at 6 months. | |
| Tertiary/Exploratory | | |
| Determine percentage of participants who achieve a clinically significant weight reduction (5% of initial weight). | Weight objectively assessed by study staff at baseline, 3 months, and 6 months. | 5% weight loss is an established indicator of clinically significant weight loss. |
| Evaluate participants perceptions of program components. | Semi-structured interviews. | We will conduct semi-structured interviews with participants to gain a deeper understanding of their perceptions of program components and their experiences in the program. |

4 STUDY DESIGN

4.1 OVERALL DESIGN

This study is a two-armed randomized controlled trial with assessments at baseline, 3 months after randomization, and 6 months after randomization. The objective is to assess the acceptability of the intervention to participants at 3 months and the feasibility of study procedures at 6 months with retention to the study as the outcome. This is a single site, Stage 1 study.

Participants will be randomly assigned to study groups by a biostatistician who is not involved with the study assessments or interventions using a random number generator. Individuals will be randomly assigned to study conditions in cohorts of approximately 30 individuals. Randomization will be concealed from participants until their first treatment session.

Participants will be randomized to receive either the tailored BELT (Better Energy through Lifestyle for Tradesmen) treatment or a standard weight loss program (Diabetes Prevention Program Group Lifestyle Balance; DPP GLB). The groups will be matched on number of weeks of treatment, mode of delivery, and contact time.

During recruitment for this study, we will conduct a randomized comparison of recruitment messages. This comparison will use a factorial design testing the effects of enhancing trust in the researchers (Trust Messaging: Yes, No) and the effects of a participant endorsement (Endorsement: Yes, No). Names and addresses for individuals from a purchased marketing list will be randomly assigned to be sent a postcard with a recruitment message matching their assigned condition. Recruitment reach will be assessed through website visits and number of participants responding to each message.

This is a feasibility study with no formal hypotheses to be tested.

4.2 SCIENTIFIC RATIONALE FOR STUDY DESIGN

This study will use a randomized design to test the feasibility of recruiting and retaining men working in blue collar occupations into a study of multiple weight loss programs. This study will use a previously tested, effective, publicly available program as the comparison group ³⁸. The benefits of using the program include that all participants will receive an active intervention and we will have data on men's performance in a standard weight loss program as well as our tailored program at the end of this study. This will be key preliminary data for future grant applications. A potential problem associated with using this control group is that participants may not be interested in a non-tailored program if a tailored program is available. This may decrease both recruitment and retention to the study.

To enhance recruitment for this study and future studies, we will use a randomized, factorial design to test the efficacy of two components of recruitment messaging. By using this factorial design, no participants will be randomized to a true control group: all participants will receive a message we believe may be effective for recruitment of this population.

4.3 JUSTIFICATION FOR INTERVENTION

This protocol is a randomized feasibility trial where participants will be randomized to a standard, non-targeted behavioral intervention (DPP GLB) or a novel tailored intervention (Better Energy through Lifestyle change for Tradesmen: BELT). The goal of the BELT intervention is to produce weight loss in via small but sustainable changes to eating and through an increase in leisure-time physical activity. The BELT intervention is a translation of our previously developed and tested intervention for men³². This intervention, like the earlier iteration, targets Social Cognitive Theory emphasized building self-efficacy for behavior change through small changes to lifestyle patterns and self-monitoring. In the earlier intervention, men lost an average of 5% of their starting weight. The intervention has been modified based on formative studies targeting men working in blue-collar occupations. Most notably, the changes include 1) delivery via online video conferencing, 2) modification of physical activity goals, 3) change to the framing of the eating modification goals (from “making 6 100-calorie changes per day” to “use a tool at nearly every time you eat”: see Eating Goals below), 4) shift from written educational materials to videos, and 5) inclusion of more language and examples that tie to blue-collar works and culture. These translations are guided by our formative work and with input from our community advisory board.

The comparison will be a group-based delivery of the Diabetes Prevention Program Group Lifestyle Balance (DPP GLB 2017). This is a manualized weight loss program designed to produce moderate weight changes through lifestyle change. The leader guides and handouts will be minimally modified for this study (e.g., changes appropriate for delivery via online group sessions vs. in-person) to provide a “standard” weight loss program comparison. The two interventions will be matched for number of group sessions and will be delivered by the same interventionist.

One of the challenges for targeting men working in blue-collar occupation in this context is that many of these men do not consider themselves overweight^{25 27} and avoid help-seeking behavior^{39 40}. To overcome this, in this study, we will test recruitment messages that will not focus on weight per se and will instead focus on the target behaviors (eating and physical activity) and outcomes reported by participants in formative work as important to them (improved energy and feeling better). The messages will explicitly target the identity of tradesmen to increase the likelihood that men working in blue-collar populations will identify with the message. This tailoring of messages theoretically increases the effort recipients exert to process the messages, as described by the Elaboration Likelihood Model⁴¹.

In our experimental comparison, this study will focus on evaluating the effects of including information to increase trust in the program in two ways. First, trust will be enhanced by increasing the transparency of the intervention development and testing process. Transparency is key to building trust in medical research.⁴² "Effects of a methodological infographic on research participants' knowledge, transparency, and trust." 40 41 In our formative work, participants nearly universally reported that they would join a program if someone personally recommended it to them. Unfortunately, relying on person recommendations is not possible in a large-scale study nor would the results be generalizable. Instead this study will test whether including an endorsement of the program by a former participant would be enough to increase interest in the program.

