5.5 STRATEGIES FOR RECRUITMENT AND RETENTION

Participants will be recruited via the postcards mailed to their homes. They will be directed to a study website where a brief description of the study will be presented. Participants recruited through the four recruitment messages will be sent to separate but identical websites. Participants who are interested will be asked to complete an online screening form. Those who appear initially eligible will be contacted to schedule a time to attend a study orientation. This orientation will allow participants the opportunity to gain information about the study and to experience the web conferencing platform (if they have not used it before). The session will describe the study and will use the motivational interviewing approach described by Kiernan and colleagues ^{44, 45, 46} to enhance engagement and retention to the study. Following this, participants will attend an in-person assessment visit where they will sign consent before completing the physical measures and self-report questionnaires. Participants who complete the baseline visit and measures will be randomized to receive either the tailored intervention or the generic intervention following a 1:1 randomization ratio.

Recruitment will be supplemented by recruitment through flyers, notices on a hospital "on-hold" line, and online recruitment messages as needed. These potential participants will be encouraged to contact the study through the study website and will go through the recruitment process described above.

All recruitment materials and plans will be reviewed and approved by the Rush University Institutional Review Board prior to implementation.

To maximize retention, we will collect multiple methods for contacting participants (e.g., email, telephone) at baseline. Participants will tentatively schedule their follow-up assessment during their initial treatment session, a method we have used in prior studies to increase retention rates. During the intervention, participants have not engaged with treatment for at least one anticipated sessions will be contacted directly by intervention staff to encourage reengagement with the program.

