6 STUDY INTERVENTION(S) OR EXPERIMENTAL MANIPULATION(S)

6.1 STUDY INTERVENTION(S) OR EXPERIMENTAL MANIPULATION(S) ADMINISTRATION

6.1.1 STUDY INTERVENTION OR EXPERIMENTAL MANIPULATION DESCRIPTION

Recruitment substudy

During recruitment for the trial, we will test the effects of recruitment messages using mailing postcards with four different recruitment messages to addresses of men believed to work in blue-collar occupations. The intervention exposure is the receipt of the postcards by potential participants. The four recruitment messages:

- Standard recruitment message alone (e.g., “Tradesmen: Boost your energy and feel better through changes to eating and physical activity!”)
- Standard message plus messages to enhance trust (e.g., “Join the BELT study: built for tradesmen with tradesmen” and “Why we are doing this: Our team wants to understand how to help men like you improve their health. We’ve developed a new program with input from men like you for men like you. It’s designed to fit into your life!”),
- Standard message plus an endorsement from a prior participant (“This is a great program...safe, thoughtful, and effective.”)
- A combined trust and endorsement message.

An identical description of the program plus a call to action “Go to [study website] to see if you are eligible!] will be included in all postcards. Participants will be sent to separate but identical websites to allow us to track the reach of the messages via the number of independent website visits. The remaining recruitment process will be identical for all participants, regardless of recruitment message received. From the website, participants can choose to be screened for eligibility and will be randomized into the trial as appropriate.

The BELT Intervention

The BELT intervention will be delivered via 16- group session conducted via web-conferencing (i.e., Zoom) supported by short, educational videos hosted on the study website. Online groups sessions will allow participants to give and receive social support from peers while also minimizing disruption to lifestyle that would be needed for a face-to-face group session. Study staff will help troubleshoot any issues using this system during the intervention. Importantly, all participants will have chance to use the platform during the online orientation session for the study. Group sessions will be 60 minutes per session and will occur weekly for months 1-3, twice in month 4, and once a month in months 5 and 6.

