6.2 FIDELITY

6.2.1 INTERVENTIONIST TRAINING AND TRACKING

The program interventionist is an registered nurse with many years of experience delivering behavior change interventions. Prior to the intervention beginning, the PI and interventionist will develop (BELT) or review (DPP GBL) all group leader guides. The PI and interventionist will meet weekly to review the previous week's sessions and review the next sessions materials.

A subset of group intervention sessions will be audio recorded and reviewed by the primary investigator using a treatment fidelity checklist. The investigator will monitor for contamination of the tailored program material appearing in the standard program but not vice versa. A subset of feedback provided to participants will also be reviewed for contamination and completeness.

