6.3 MEASURES TO MINIMIZE BIAS: RANDOMIZATION AND BLINDING

Randomization to treatment conditions for the recruitment message substudy will be conducted by the study Principal Investigator using a random number generator. Participants will not be blind to the study condition but will be blind to hypotheses. Staff cannot be blinded to study arm as they will need to ask which recruitment message was received.

In the main trial, randomization to treatment condition will be conducted by a statistician not involved with treatment delivery. Randomization will be revealed to participants at their first treatment session. Outcome assessors will be blind to treatment assignment.

Though it is not possible to blind participants to the nature of the treatment they are receiving, both arms will be named and described as (and truly are) active treatments to eliminate expectancy effects. As both arms will receiving information remotely, risk of contamination is minimal.

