9.2 SAMPLE SIZE DETERMINATION

This is a feasibility study. No formal sample size estimations were conducted. Instead the sample size was selected to produce appropriate size treatment groups ($n = 15$) for two interventions across two cohorts ($N = 60$).

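### One interventionist leads both arms live, so session time is tied to arm within each cohort; assigning slots at random and reversing them in cohort 2 would keep most or all of a slot effect out of the pooled arm differences.

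*Combined protocol and SAP*

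**What the plan says.** **Leader.** Section 4.3 states that the two programmes "will be matched for number of group sessions and will be delivered by the same interventionist". Section 6.2.1 describes a single person: "The program interventionist is an registered nurse with many years of experience delivering behavior change interventions".

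**Groups.** Section 4.1: "Individuals will be randomly assigned to study conditions in cohorts of approximately 30 individuals". Section 5.5 randomises men to "the tailored intervention or the generic intervention following a 1:1 randomization ratio". Section 9.2 bases the total on "appropriate size treatment groups ($n = 15$) for two interventions across two cohorts ($N = 60".

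**Format.** Sections 6.1.1 and 6.1.2 describe 16 live one-hour Zoom groups in both arms, on the same weekly-then-tapering frequency.

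**Matching.** Section 4.1: "The groups will be matched on number of weeks of treatment, mode of delivery, and contact time". Section 4.3 adds the number of sessions. Day and hour are not among the matched features.

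**Bias control.** Section 6.3 covers randomisation, blinding and contamination. It also says "Randomization will be revealed to participants at their first treatment session". No section gives session times, says how a slot is assigned to an arm, or alternates slots between cohorts.

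**Use of the arm comparison.** Section 9.4.2 reports acceptability descriptively. Section 9.4.3 compares 6-month completion across arms descriptively. Section 9.4.9 explores between-group effect sizes for 5% weight loss.

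**The concern.** The design takes care to equalise the arms on everything except programme content, and a shared leader is part of that. The shared leader, however, forces the arms into different session times, and time is then the one delivery feature left uncontrolled.

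The men must work more than 20 hours a week (section 5.1). The sponsor's formative work (section 2.2) found that a programme has to fit into daily life, so an awkward slot could plausibly lower satisfaction with whichever programme occupies it. A descriptive difference between BELT and DPP GLB could then reflect the timetable, in either direction. Section 4.2 expects that a non-tailored arm may retain fewer men; a poor slot for that arm could look the same. Section 4.2 also intends the results as preliminary data for later grant applications, and a confounded difference would carry over into them.

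**Working it through.** **1. Reproduce the plan's figure.** 15 per group × 2 interventions × 2 cohorts = 60, as in section 9.2. That is 60/15 = 4 groups, 2 per cohort, so 1 per arm per cohort. The last step is derived from section 9.2 and the 1:1 ratio; the plan does not state it in words.

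**2. Must the slots differ?** Sections 4.3 and 6.2.1 give one leader. Sections 6.1.1 and 6.1.2 give live sessions in both arms at the same frequency. One leader cannot run both at once, so the two groups of a cohort meet on different days or at different hours.

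**3. Can arm and slot be separated?** Code each of the four groups as (arm, cohort, slot), with 15 men each and an intercept in the model.

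- Same slot per arm in both cohorts: (0,0,0), (1,0,1), (0,1,0), (1,1,1). The arm–slot correlation is 1.0 and the design matrix has rank 3 of 4, so the two effects cannot be separated.
- Slots reversed in cohort 2: (0,0,0), (1,0,1), (0,1,1), (1,1,0). The correlation is 0 and the rank is 4 of 4.

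**4. Bias in the pooled arm difference.** Let s be the additive slot effect and n1, n2 the cohort sizes, each split 1:1. The bias is s times the difference between arms in the share of men in the better slot.

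- Slots kept: s × (1 − 0) = s, which is 100% of the slot effect.
- Slots reversed: s × (n1 − n2)/(n1 + n2). Cohorts of 30 and 30 give 0. Cohorts of 34 and 26 give 8/60 = 0.13, so about 13% of s remains.

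**5. Scale.** The documents give no slot effect, SD or retention rate, so these are assumptions. Standard errors are for 30 per arm and ignore clustering by group.

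- Satisfaction: SE = √(2/30) = 0.26 SD. With slots kept, an assumed s of 0.1, 0.2, 0.3 or 0.5 SD shifts the arm difference by the same 0.1, 0.2, 0.3 or 0.5 SD.
- Retention: SE = √(2p(1 − p)/30), which is 11.8, 10.3 or 7.7 percentage points at assumed retention of 70%, 80% or 90%.

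**6. What the reversal cannot do.** With 15 per arm in a cohort, the SE of a within-cohort difference is √(2/15) = 0.37 SD, and of the contrast between the two cohorts' differences √(4/15) = 0.52 SD. That contrast would equal 2s plus any arm-by-cohort difference (season, group dynamics, leader learning). Even s = 0.3 SD gives 0.6 SD, little more than one SE, and it cannot be told apart from the other sources.

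**The case against.** The strongest reply is that the bias is possible, not shown. It needs one slot to be materially better and the same arm to hold it in both cohorts, and the plan says neither. The same hour on adjacent weekdays would satisfy every section. Timetables may also sit in the Manual of Procedures that section 10.1.10 mentions, which is not available here. The study is a feasibility trial without formal hypotheses (sections 4.1 and 9.1), so no test is invalidated. All of this stands, and it limits the point to a cheap improvement. It does not remove the point: within a cohort the confounding follows from the design, and the arms are compared, even if descriptively.

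Four stronger readings are tempting, and the documents do not support them.

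- *A man who cannot make his slot is lost from the trial.* Section 7.1 keeps men who stop the intervention in all later assessments, section 7.3 follows every randomised man whatever his participation, and section 9.3 analyses by intention to treat. He may miss sessions, but he stays in follow-up.
- *Every Aim 1 outcome is biased.* The Aim 1 endpoint is satisfaction at 3 months. Retention belongs to a secondary objective and is measured by a weight assessment at an in-person visit, so any slot effect on it is indirect. Attendance is recorded (section 6.4) but is not an endpoint in section 3.
- *Men should be randomised only if free for both slots.* Such a rule could cut enrolment, which is the Aim 2 endpoint, and select men with flexible schedules in a population already described as unlikely to take part.
- *Reversing the slots would reveal the slot effect.* It would not, because slot is then aliased with arm-by-cohort differences.

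**Conclusion.** The point holds as a low-cost design improvement. Slot is confounded with arm within each cohort, and nothing in the plan prevents the same alignment in both. In that case the whole slot effect enters the pooled descriptive differences in satisfaction, retention and 5% weight loss. The documents do not allow its size to be estimated, and it may be small; an assumed 0.2 to 0.3 SD would be about as large as the sampling error of the satisfaction difference.

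The conclusion rests on three things: a single leader for both arms, one group per arm per cohort (derived from section 9.2), and no slot rule elsewhere in the documents. The contact guidelines in section 5.5 use the plural for interventionists, but they concern reaching men who have missed sessions and do not alter the statement in section 4.3.

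**What to change.** Add to section 4.1: two weekly slots are fixed for each cohort before randomisation; the statistician assigns arm to slot at random in cohort 1 and reverses the assignment in cohort 2; the same two slots are used in both cohorts where feasible; slot times are recorded. Add to sections 9.4.2 and 9.4.3 that satisfaction and retention are also shown by cohort.

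Reversal is better than a fresh random assignment in cohort 2, which would repeat the cohort 1 alignment with probability 1/2. Using the same two slots matters because the cancellation assumes that the slot effect is additive and the same in both cohorts.

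The cost is a few sentences and a minor scheduling constraint on the interventionist. N stays at 60 and eligibility does not change. The reversal removes additive slot bias when cohorts are equal (all but about 13% of it at 34 and 26). It does not remove variation between the four groups, which remains a limit with two groups per arm. It has to be settled before the sessions of cohort 2 are scheduled.
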